Study Protocol and Statistical Analysis Plan

Heat Waves in the Elderly: Reducing Thermal and Cardiovascular Consequences

NCT04538144

August 23rd, 2024

**Experimental Protocol:** All experimental trials began between 8:00 and 10:00 to avoid diurnal variations. Before experimental trials, participants were instructed to eat a light breakfast (without caffeinated beverages) on the morning of testing. Alcoholic beverages and aerobic/resistance exercise were prohibited 24 hours before testing. Upon arrival, participants provided a urine sample and weighed themselves nude. A euhydrated state before each trial was confirmed by a urine specific gravity value  $\leq 1.020$  (Atago Inc., Bellevue, WA). If urine specific gravity was between 1.020 and 1.024, participants ingested 500 mL of water before testing. If their urine specific gravity was  $\geq 1.025$ , the trial was rescheduled to a later date. Participants rested in a temperate environment ( $\sim 22^{\circ}\text{C}$  and 40% humidity) for at least one hour while baseline measurements (e.g., heart rate, blood pressure, forearm blood flow, etc.) were performed. Following baseline measurements, participants entered the environmental chamber set to one of the following two extreme heat simulations: 1) DRY ( $47^{\circ}\text{C}$  and 15% humidity; reflective of the 2018 Los Angeles heatwave) and 2) HUMID ( $41^{\circ}\text{C}$  and 40% humidity; reflective of the 1995 Chicago heatwave). The duration of each exposure was 3 hours, which represents the approximate duration of peak environmental temperatures during a heatwave (4, 31). Before instrumentation, participants' body mass was measured using a precision balance scale with  $\pm 10$  g accuracy (Mettler Toledo, OH). After a brief period ( $\sim 5$ -minutes) of instrumentation, participants were seated in a semi-recumbent position on a chair with a breathable fabric thereby reducing impediments for thermal exchange from the regions in contact with the chair. To reduce the influence of clothing on thermoregulatory responses, participants wore athletic shorts (males) or athletic shorts and a sports bra (females). To decrease the effect of dehydration, participants consumed 3 mL/kg body mass of tap temperature water ( $14$ - $16^{\circ}\text{C}$ ) every hour during the extreme heat simulation. This level of fluid ingestion was based on pilot data and was selected to maintain hydration to a level that would not compromise thermoregulatory, perceptual, or cardiovascular responses during heat exposure (16, 54, 55). Tap water temperature was used to mimic the water available to individuals during an actual heatwave. Following the extreme heat simulation,

participants were de-instrumented and provided a towel to wipe off excess sweat before they weighed themselves nude.

*Insert Figure 1 here*

**Metabolic Heat Production:** Participants performed seven 5-minute bouts of light physical activity (either cycling: n=39 or walking: n=1) dispersed throughout the 3-hour extreme heat exposure (Figure 1). The intensity of the activity was maintained at a working metabolic rate of ~3 METs to mimic activities of daily living such as cooking, cleaning, carrying groceries, moving around the home, etc. (1). Metabolic heat generation was verified using indirect calorimetry (PARVO Medics True-One Metabolic Measurement System, Parvo Medics, Salt Lake City, UT), with metabolic gases being collected during the first two 5-minute periods of exercise. That identified workload was used for all subsequent exercise bouts. The average rate of oxygen consumption, respiratory exchange ratio, and workload were used to determine metabolic heat production, which was calculated using standard formulae (19).

**Instrumentation:** Core temperature was measured via rectal temperature using a general-purpose thermocouple probe inserted 10 cm beyond the anal sphincter (Mon-a-therm, Mallinckrodt Medical, St. Louis, MO) (Young: n=17, Older: n=8) or a telemetric pill (e-Celsius performance pill ®, BodyCap®, Caen, France) used as a rectal suppository (Young: n=1, Older: n=1). If participants did not consent to rectal temperature measurement, or if there were technical issues with the rectal thermocouple probe, core temperature was measured using an orally ingested telemetric pill (Young: n=2, Older: n=11). In these participants, the ingestible telemetric pill was taken no less than 1 hour before beginning the extreme heat exposure. Importantly the time following ingestion of the telemetric pill (e.g., between 1 and 12 hours) does not influence the validity of pill temperature as an index of core temperature (49). In addition, there is good agreeability amongst these methods to measure core temperature (10, 29), and for participants who had simultaneous measures of pill and rectal temperature in this study (n=25) the intraclass correlation coefficient was 0.87. Mean skin temperature was obtained as the weighted average

of local temperatures measured via the chest (22%), upper back (21%), lower back (19%), abdomen (14%), anterior thigh (13%), and calf (11%) (58).

Forearm blood flow, as a surrogate of changes in skin blood flow, was measured from brachial artery blood velocity and diameter values obtained by duplex ultrasonography (iE33/EPIQ 7, Philips Medical Systems, Andover, MA). A linear transducer (L12-3, Philips Medical Systems, Andover, MA), operating at an insonation angle of 60°, was placed proximal to the brachial artery bifurcation where the best spatial resolution of the artery could be obtained. Imaging was performed by the same sonographer throughout each heat exposure, and to aid in consistency between measurements sonographers used anatomical landmarks (e.g., ~9 cm proximal to the medical epicondyle) to ensure similar probe placement. Blood velocity was measured using time-averaged mean velocity from pulsed-wave Doppler ultrasound. Offline 2D images of the brachial artery were used to measure vessel diameter at end-diastole. Brachial artery diameter and blood flow velocity were measured from recordings of 5 consecutive cardiac cycles at baseline and in the final 15 minutes of extreme heat exposure. Blood flow velocity and brachial artery diameter measurements were used to calculate forearm blood flow using a standard formula:

$$\text{Flow (mL/minute)} = v \cdot \pi \cdot \left(\frac{d^2}{4}\right) \cdot 60 \quad \text{Eq 1}$$

Where  $v$  is velocity in m/s and  $d$  is diameter in cm.

Heart rate was obtained from a 6-lead electrocardiogram (GE Medical Systems, Madison, WI). Blood pressure was measured by automated auscultation of the brachial artery (Tango+, SunTech Medical, Morrisville, NC, USA). Local sweat rate was measured on the upper back using a ventilated capsule technique where anhydrous compressed nitrogen was passed through the capsule at a flow rate of ~300 mL/min. The water content of the nitrogen gas was then measured using capacitance hygrometers (Vaisala, Woburn, WA, USA) and normalized for the area under the capsule.

Thermal perception was measured using an 8-point scale, with 0.5 increments ranging from 0.0 ('unbearably 'cold'), 4 ('comfortable'), to 8.0 ("unbearably hot"). At the start and end of each extreme heat exposure, participants were given a modified environmental symptom questionnaire (53) to assess symptoms commonly associated with environmental stress such as "I feel lightheaded", "I have a headache", "I feel dizzy", "I feel thirsty", "I feel weak", "I feel grumpy", "It is hard to breathe", "I have a muscle cramp", "I feel tired", "I feel nauseous", "I feel hot", "I have trouble concentrating", "I feel 'goose bumps' or chills", and "I can play at my best", on a scale of 1 ("not at all") to 6 ("extreme").

**Blood Sampling and Analysis:** Blood was taken from an arm vein after 30 minutes of supine rest at baseline and the end of the extreme heat simulations. We measured hematocrit (microcapillary technique) and hemoglobin (ABL90 Flex, Radiometer, Brønshøj, Denmark) to calculate changes in plasma volume using the Dill and Costill (22) equation. Blood samples were centrifuged to isolate plasma and aliquots of plasma were sent to a nearby laboratory (Texas Health Presbyterian, Dallas TX) to determine plasma osmolality (Abbott Alinity, IL, USA).

**Calculations:** We calculated mean body temperature as:

$$\text{Mean body temperature } (\text{°C}) = 0.8T_{\text{core}} \times 0.2T_{\text{skin}} \quad \text{Eq 2}$$

Where  $T_{\text{core}}$  and  $T_{\text{skin}}$  are core temperature and mean skin temperature, respectively.

We calculated mean arterial pressure (MAP) as:

$$\text{MAP } (\text{mmHg}) = \frac{\text{SBP}}{3} + \left( \text{DBP} \times \frac{2}{3} \right) \quad \text{Eq 3}$$

Where SBP and DBP are systolic and diastolic blood pressure, respectively.

We calculated forearm vascular conductance by dividing forearm blood flow by MAP. We calculated body mass loss as the difference in nude body weight (Mettler Toledo, OH) between pre- and post-extreme heat exposure, and whole body sweat loss (WBSL) after correcting for fluid ingestion and urine output, which was collected and measured for volume. We calculated whole body sweat rate by dividing the whole body sweat loss by total heat exposure time.

**Data Acquisition:** Rectal temperature, skin temperature, local sweat rate, and heart rate were sampled at 250 Hz (Biopac MP150, Santa Barbara, CA) and converted into 1-minute averages for data analysis. Core temperature measured via the telemetric pill (both ingested and as a suppository) was sampled every 30 seconds, and blood pressure was measured every 15 minutes during heat exposures.

**Statistical Analyses:** A power calculation was performed to detect a 0.5°C difference in the increase in core temperature between groups, with a standard deviation of that increase being 0.5°C. Based upon these estimates, and with an alpha of 0.05, 20 participants (10 participants per age group) would provide power of >0.80 to detect differences between age groups in the change in core temperature (power analyses from: NCSS PASS 2019). However, we enrolled 40 participants (20 participants per age group, with each age group comprising 10 males and 10 females) to account for possible attrition/missing data and to increase the capability to detect differences in other outcome variables that may have a greater degree of variability than core temperature. Due to technical difficulties, we were unable to obtain some measurements (e.g., skin temperature, local sweat rate, blood pressure, and limb blood flow) at either baseline or at the end of the extreme heat exposures in some participants. Similarly, we were unable to obtain metabolic heat production data in one young and one older participant. These missing data were excluded from final analyses, and the number of participants included for each variable is indicated in text, tables, and figures where appropriate. Before analyses, data were assessed to confirm that they met model assumptions (i.e., normality, equality of variance). Within each extreme heat simulation, we analyzed data using linear mixed effect models with main effects of time (within factor) and group (between factor; older vs young) or unpaired t-tests (two-tailed), as appropriate. Statistical analyses were performed in R studio (Version 2022.07.1), and graphs were generated using GraphPad Prism 9.4 (GraphPad Software Inc., La Jolla, CA, USA). Data in text, tables, and figures are presented as means  $\pm$  standard deviations. Statistical significance was set *a priori* to  $p < 0.05$ .

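### Eq 1 for forearm blood flow does not balance: with velocity in m/s and diameter in cm, the result labelled mL/min is 100-fold too small

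*Combined protocol and SAP*

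**What the plan says.** The forearm blood flow paragraph under Instrumentation says that brachial artery velocity and diameter "were used to calculate forearm blood flow using a standard formula". That formula is Eq 1: flow in mL per minute equals v·π·(d²/4)·60. The definition line under it states that v "is velocity in m/s and" that d "is diameter in cm". No other section gives a unit for velocity.

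Two later statements depend on Eq 1:

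- **Calculations:** "We calculated forearm vascular conductance by dividing forearm blood flow by MAP".
- **Statistical Analyses:** "Data in text, tables, and figures are presented as means", with standard deviations. The tests are linear mixed models with time and group, or two-sided unpaired t-tests.

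**The concern.** Eq 1 is the document's only rule for deriving forearm blood flow, which serves as the stand-in for skin blood flow. Conductance is built from it. If the stated units do not produce the stated output unit, anyone who follows the rule literally could obtain wrong absolute values for two outcomes. Because results are to be shown as means and standard deviations, those absolute values are what a reader would see and compare with other work.

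The document reports no velocity, diameter, flow or conductance values. A reader therefore cannot tell a mislabelled unit in the text from an error carried into the data.

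**Working it through.** **Inputs from the document.** Output unit mL/min; v in m/s; d in cm; only conversion constant 60 (all from Eq 1 and its definition line). Conductance = flow ÷ MAP (Calculations). There is no reported flow value to reproduce.

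**Step 1: units as written.**

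- v·π·(d²/4)·60 has units (m/s) × cm² × (60 s/min), which is m·cm²/min.
- 1 m = 100 cm, so 1 m·cm² = 100 cm³ = 100 mL.
- Each numerical unit of the result is therefore 100 mL/min, not 1 mL/min. The label understates flow by a factor of 100 for any v and d.

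**Step 2: units with v in cm/s.** (cm/s) × cm² × (60 s/min) = cm³/min = mL/min. The equation balances.

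**Step 3: numerical check.** The velocities and diameters are assumptions, since the document gives none.

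| v (m/s) | d (cm) | Eq 1 as written | v in cm/s (mL/min) | Ratio |
|---|---|---|---|---|
| 0.05 | 0.35 | 0.289 | 28.9 | 100 |
| 0.10 | 0.40 | 0.754 | 75.4 | 100 |
| 0.20 | 0.45 | 1.91 | 190.9 | 100 |
| 0.40 | 0.50 | 4.71 | 471.2 | 100 |

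For the second row:

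- As written: 0.10 × π × 0.40²/4 × 60 = 0.754.
- With cm/s: 10 × π × 0.40²/4 × 60 = 75.4.
- Entirely in SI units: 0.10 × π × 0.0040²/4 × 60 × 1,000,000 mL per m³ = 75.4 mL/min, which agrees with the cm/s result.

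**Step 4: conductance.** With an assumed MAP of 90 mmHg and the second-row inputs, 0.754/90 = 0.0084 as written, against 75.4/90 = 0.84 mL/min/mmHg. The ratio is again 100.

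**Step 5: what a constant factor does to the analysis.** Suppose every recorded flow is Y/100 instead of Y.

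- Means, standard deviations, standard errors and group differences are all divided by 100.
- A t statistic is (difference/100) ÷ (standard error/100), which is unchanged. The same holds for each fixed effect in a linear mixed model, because the estimate and its standard error scale together. The p-values do not move.
- A percent change is (Y₂/100 − Y₁/100) ÷ (Y₁/100), which is unchanged.
- The power calculation concerns the rise in core temperature and does not use Eq 1.

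This invariance requires the same velocity unit in every record. The document does not state that.

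**The case against.** The strongest reply is that this is a label slip with no consequence. The text calls Eq 1 a standard formula, d is in cm, the output is in mL/min, and everything fits if v is in cm/s. Nothing shows that any result was miscalculated. If the recorded velocities were in cm/s, the computed flows are correct. A value such as 0.754 mL/min in place of 75.4 would also probably prompt a unit check. No test, p-value, percent change or sample size depends on the point.

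Most of this stands. A mislabelled unit is the likelier reading, and the effect on inference is nil if one unit was used throughout. A character lost when the text was read from PDF cannot be strictly excluded either, though nothing around the unit looks damaged and the cm for diameter came through intact.

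The reply does not remove the need for a correction. The derivation rule for an outcome is wrong as written, it passes into a second outcome, and the document alone cannot show that the data escaped the error.

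**Conclusion.** The concern holds. With the units stated, Eq 1 yields values exactly 100 times too small for its mL/min label, and forearm vascular conductance inherits the factor. The factor follows from the document's own units and does not depend on the assumed velocities, diameters or MAP, which only illustrate it.

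Whether any computed result is wrong depends on whether velocities were entered in m/s without conversion, which the document does not show. If they were, absolute means, standard deviations and age-group differences for flow and conductance are wrong by a factor of 100. If they were in cm/s, only the text is wrong. Provided one unit was used for all records, the hypothesis tests and percent changes stand in either case. The matter should be corrected, but it does not threaten the trial's inferences.

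**What to change.** 1. In the definition line of Eq 1, give v in cm/s. Alternatively, keep m/s and multiply the right-hand side by 100.
2. Confirm the velocity unit in the analysis data set, and that it is the same for every participant and time point. Instrumentation names two ultrasound systems, so the check should cover records from both.
3. If m/s was used without conversion, recompute forearm blood flow and forearm vascular conductance and correct the absolute summaries. Otherwise change the label only.

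The cost is one edit to the text and one check of the data set, with a rescaling only if the check calls for it. Design, sample size and planned tests do not change.

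### Equation 2 multiplies the core and skin terms where a weighted sum is evidently meant, so mean body temperature as printed is not a temperature

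*Combined protocol and SAP*

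**What the plan says.** The Calculations section gives Eq 2 for mean body temperature, labelled in °C, as "0.8T_{\text{core}} \times 0.2T_{\text{skin". The line beneath it explains that the two symbols "are core temperature and mean skin temperature, respectively". No other part of the document defines the variable, corrects the formula or reports a value for it.

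Two other weighted averages appear in the plan, and both are additive:

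- **Mean skin temperature (Instrumentation).** "Mean skin temperature was obtained as the weighted average" of six local sites, with weights "chest (22%), upper back (21%), lower back (19%), abdomen (14%), anterior thigh (13%), and calf (11"%).
- **Mean arterial pressure (Eq 3, directly after Eq 2).** One third of systolic pressure plus two thirds of diastolic pressure.

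The sample size in Statistical Analyses rests on core temperature alone: "A power calculation was performed to detect a 0.5°C difference in the increase in core temperature between groups".

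**The concern.** Eq 2 is an operative formula that an analyst would code from. Followed literally, it gives a number that is neither in the stated unit nor a mean of its two inputs.

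The error is more than a change of scale. In a product the coefficients 0.8 and 0.2 merge into one constant, 0.16, and the fourfold weighting of core over skin disappears. If the code followed the printed formula, an age-group comparison of this variable would largely reflect skin temperature, when the weights are meant to make core temperature dominate.

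The documents name the statistical software but do not show the code, so a reader cannot tell which form was used.

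**Working it through.** **Inputs.** The coefficients 0.8 and 0.2, the operator and the unit come from Eq 2. The documents give no core or skin temperatures, so I assume core 37–38°C and skin 33–37°C for illustration. There is no published mean body temperature to reproduce.

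**Unit and weights**

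- As printed: 0.8·Tcore × 0.2·Tskin = 0.16·Tcore·Tskin, in °C².
- As a sum: 0.8·Tcore + 0.2·Tskin, in °C.
- Eq 2 weights: 0.8 + 0.2 = 1. Eq 3 weights: 1/3 + 2/3 = 1. Skin-site weights: 22 + 21 + 19 + 14 + 13 + 11 = 100%.

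**Can the product ever be a mean?** A mean must not exceed the larger of its inputs. If core is the larger, 0.16·Tcore·Tskin ≤ Tcore requires Tskin ≤ 1/0.16 = 6.25°C. If skin is the larger, the same bound applies to Tcore. No plausible body temperature meets it, so this step does not depend on the assumed range.

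**Values over the assumed range**

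| Core / skin (°C) | Product, as printed | Sum (°C) | Core:skin slope ratio of product (Tskin/Tcore) |
|---|---|---|---|
| 37 / 33 | 195.36 | 36.2 | 0.892 |
| 38 / 33 | 200.64 | 37.0 | 0.868 |
| 37 / 37 | 219.04 | 37.0 | 1.000 |
| 38 / 37 | 224.96 | 37.8 | 0.974 |

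The slope ratio of the sum is 0.8/0.2 = 4.0 throughout. A wider assumed range, from 36.5/32 to 38.5/38, gives 186.88 to 234.08 for the product and 35.6 to 38.4°C for the sum.

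**Effect of a 0.5°C step at core 37.5, skin 35.** There the product is 210.0 and the sum 37.0°C. The step size is for convenience; the plan uses 0.5°C only for the between-group difference in core temperature rise.

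- Core +0.5: the product rises by 0.16 × 0.5 × 35 = 2.80; the sum by 0.8 × 0.5 = 0.40°C.
- Skin +0.5: the product rises by 0.16 × 0.5 × 37.5 = 3.00; the sum by 0.2 × 0.5 = 0.10°C.

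**Effect on a change from baseline.** Take a move from 37/33 to 38/37.

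- Sum: 0.8 × 1 + 0.2 × 4 = 0.8 + 0.8 = 1.6°C, so skin accounts for half.
- Product: 0.16 × (38 × 37 − 37 × 33) = 0.16 × 185 = 29.6. At the midpoints this splits into 0.16 × 1 × 35 = 5.6 from core and 0.16 × 4 × 37.5 = 24.0 from skin, so skin accounts for 24.0/29.6 = 81%.

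**The case against.** The text was read from PDF by a program, and a misread plus sign would not be an error in the plan. Eq 3, which follows at once, shows both a plus and a multiplication sign correctly. That makes a misread less likely but does not exclude it, so the source page should be checked first.

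Nothing suggests that the product was ever computed. Values near 200 labelled °C would stand out in any table or graph, and the intended formula is easily inferred from the unit, the name and the weights. This stands. The figures in the working describe what the printed formula does, not an error shown in any result, and an alert reader could recover the right formula.

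The consequences are also narrow. The documents do not name mean body temperature as a primary or secondary outcome, and the text reports work already done, so a correction changes no future conduct. This too stands, and it is why the point is rated minor. It does not make the printed definition correct, and that definition is the only one given.

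**Conclusion.** The concern holds. As it appears in the document, Eq 2 is wrong on the plan's own terms, and a weighted sum is evidently intended.

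Taken literally, it gives about 195–225 where the sum gives 36.2–37.8°C, and it replaces a 4:1 core-to-skin weighting with roughly 0.87–1.00 to 1. Those ranges rest on the assumed temperatures. The unit failure, the weights summing to 1 and the 6.25°C bound do not.

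The effect is confined to this one derived variable. The power calculation, the core temperature comparison, mean arterial pressure, forearm vascular conductance and sweat rate do not use Eq 2. Severity is minor. Confidence is high that the formula as supplied is wrong; whether the analysis was affected cannot be judged from the documents.

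**What to change.** 1. Check the symbol on the source page. If it is a multiplication sign there, correct Eq 2 to: mean body temperature (°C) = 0.8·Tcore + 0.2·Tskin.
2. Confirm that the analysis code used the sum. As a quick screen, each value must lie between the same participant's skin and core temperatures at the same time point. That would expose the product but not swapped weights, so also recompute a few stored values directly from their inputs.
3. Re-derive the variable and repeat its age-group comparison only if the product was used.

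The cost is one symbol and a short code check, with no re-analysis unless step 2 fails.

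### Whole-body sweat loss, sweat rate and body mass loss have no stated body-size normalisation and no body-size term in the age comparison, so any difference in body mass between the groups enters the contrast.

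*Combined protocol and SAP*

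**What the plan says.** Three outcomes are defined in the Calculations section. On body mass loss: "We calculated body mass loss as the difference in nude body weight (Mettler Toledo, OH) between pre- and post-extreme heat exposure". From that the plan derives "whole body sweat loss (WBSL) after correcting for fluid ingestion and urine output". Then: "We calculated whole body sweat rate by dividing the whole body sweat loss by total heat exposure time". No step divides by body mass or surface area, or expresses the result as a percentage of starting mass.

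Statistical Analyses gives one rule for all data, applied within each heat simulation: "linear mixed effect models with main effects of time (within factor) and group (between factor; older vs young) or unpaired t-tests (two-tailed), as appropriate". It names no covariate.

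Elsewhere the plan does scale for size. Under Experimental Protocol, "participants consumed 3 mL/kg body mass of tap temperature water" each hour. Under Instrumentation, local sweat rate is expressed relative to capsule area. Statistical Analyses also states that each age group has 10 males and 10 females. Nude mass is taken on arrival for each trial.

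**The concern.** Larger people can be expected to lose more sweat in absolute terms, and here they also drink more, because water is given per kg. Age group is an observed characteristic, so nothing in the design makes mean body mass equal in older and young participants. Equal numbers of each sex remove the sex-related part of a size difference but do not match mass within sex.

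If one group is heavier, an unadjusted comparison can show more sweat or mass loss in that group without any age effect on sweating. The error can also run the other way. Suppose older participants sweat 20% less per kg but are 10% heavier: under proportional scaling the ratio of absolute losses is 0.80 × 1.10 = 0.88, so a 20% deficit shows as 12%. Even where mean mass is balanced, the spread in mass stays in the residual and widens the interval for the age contrast.

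What is at stake is how these secondary sweating outcomes are interpreted as an account of age differences in heat strain.

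**Working it through.** **Plan's own figure.** There is none for these outcomes. The only design figure is the power statement for core temperature, which is not an input here. The documents give no body mass by group, no sweat SD and no scaling law.

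**Input from the documents.** n = 20 per group; two-tailed unpaired t-test; threshold 0.05 (Statistical Analyses).

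**Assumed inputs.**
- Sweat loss scales as mass^b, with b from 0.67 to 1.
- Between-person CV of sweat loss: 25-30%.
- Imbalance in mean mass, r: 5%, 10% or 15%.
- No age effect at a given mass.

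**Step 1: spurious difference.** Relative difference = (1 + r)^b − 1. At r = 0.10:
- b = 1: 1.10 − 1 = 10%.
- b = 0.67: 1.10^0.67 − 1 = 1.066 − 1 = 6.6%.

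**Step 2: rejection rate.** Standardised difference d = relative difference / CV. Noncentrality = d × √(n/2) = d × √10, with 38 degrees of freedom. At r = 0.10:
- b = 1, CV 30%: d = 0.33, noncentrality 1.05, rejection 0.177.
- b = 1, CV 25%: d = 0.40, noncentrality 1.26, rejection 0.234.
- b = 0.67, CV 30%: d = 0.22, noncentrality 0.69, rejection 0.104.
- b = 0.67, CV 25%: d = 0.26, noncentrality 0.83, rejection 0.129.

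The same calculation across imbalances gives these rejection rates (CV 30% to CV 25%):

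| Mass imbalance | b = 0.67 | b = 1 |
|---|---|---|
| 0% | 0.05 | 0.05 |
| 5% | 0.063-0.069 | 0.081-0.095 |
| 10% | 0.104-0.129 | 0.177-0.234 |
| 15% | 0.172-0.228 | 0.338-0.456 |

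**Step 3: precision when mean mass is balanced.** Assume mass CV 15-20% and sweat CV 30%. Share of variance explained by mass = (b × CV of mass / CV of sweat)²; SE ratio = √(1 − share).
- b = 1: (0.15/0.30)² = 0.25 to (0.20/0.30)² = 0.44; SE ratio 0.87 to 0.75, a narrowing of 13-25%.
- b = 0.67: 0.335² = 0.11 to 0.447² = 0.20; SE ratio 0.94 to 0.89, a narrowing of 6-11%.

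**Step 4: does dividing by kg solve it?** Under b = 1, yes: in a 20,000-run simulation the per-kg t-test rejected about 5% of the time at every imbalance from 0 to 20%. Under b = 0.67 it over-corrects: a group 10% heavier has a per-kg ratio of 1.10^0.67 / 1.10 = 0.969, a spurious deficit of about 3%. A mass covariate does not impose proportionality in this way.

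**The case against.** **Absolute units and an unadjusted test are inferred.** No units are printed for these three outcomes, and the test for each is not named; the analysis sentence is general and leaves the choice open. This stands. A reader might infer that the plan states an unadjusted comparison in absolute units. The documents support only that no normalisation and no body-size term are stated, although the absolute reading is the natural one.

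**Sex is balanced.** This stands in part. It removes one source of size difference, but not differences in mass within sex.

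**The magnitude is assumed, and proportional scaling is the unfavourable case.** This stands. The chamber is at 47°C or 41°C, and activity is limited to seven 5-minute bouts in 3 hours, so environmental heat exchange, which depends on surface area, may matter. That is why the figures run from mass^0.67 to mass^1. Quoting only the proportional-scaling result at a 10% imbalance, 18-23%, would overstate what is known.

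**It is partly a choice of estimand.** Absolute loss says how much fluid each group lost. If body size differs because of age, adjustment removes part of the age-group difference. This stands, and it is a reason to report both contrasts rather than demote the absolute one. It does not make the absolute contrast a measure of age-related sweating at a given body size.

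**The outcomes are secondary.** Core temperature is the powered outcome, and local sweat rate already offers a sweating measure scaled by area, though at one site. This limits the importance of the point but does not answer it.

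**Conclusion.** The point holds as a gap in the analysis of three secondary outcomes. Their definitions carry no body-size divisor, the stated models carry no body-size term, and the groups are neither randomised nor described as matched on mass.

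Its size cannot be determined from the documents. On the assumptions above, a 10% mass imbalance produces a spurious difference of 6.6-10% and a rejection rate of about 10-23% instead of 5%. With balanced mass there is no bias, and adjustment would narrow the standard error by about 6-25%.

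Two stronger conclusions are tempting and unsupported. One is that a reported age difference in sweating is an artefact of body size: with no masses given, neither the presence nor the direction of bias is known. The other is that the core temperature comparison is compromised: nothing here bears on it.

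**What to change.** In Statistical Analyses, for whole-body sweat loss and whole-body sweat rate, add a linear model within each heat simulation: outcome on group plus pre-exposure nude body mass. Report it beside the absolute comparison, not in place of it. Report body mass loss also as a percentage of pre-exposure mass. State the units of all three outcomes and give body mass by age group, so that a reader can see whether an imbalance exists.

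Prefer the covariate to per-kg division for the sweat outcomes, since division is unbiased only under proportional scaling. The percentage for mass loss has the same limit and should be read beside the absolute value.

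The cost is one degree of freedom per model and a short addition to the text; nude mass is already measured, so no new data are needed. The document is written in the past tense. If the analysis is already complete, the adjusted results should be labelled post hoc.
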